6.5.2 Secondary Efficacy Endpoints

The secondary efficacy endpoints are identified in Section 2, [Table 1](#).

6.5.3 Exploratory Efficacy Endpoints

The exploratory efficacy endpoints are identified in Section 2, [Table 1](#).

6.5.4 Estimands

The primary efficacy study estimand is the difference in means between balovaptan and placebo in the change from baseline at Week 24 in Vineland-II 2DC score in the targeted ASD adult population, as identified by the study inclusion and exclusion criteria.

Intercurrent events that occur after treatment initiation and either preclude observation of the variable or affect its interpretation might occur. The appropriate strategy to treat intercurrent events will be described in the Statistical Analysis Plan. As a general principle, if treatment discontinuation is due to:

- Study drug-related reasons (e.g., treatment-related adverse event, or lack of efficacy) then the actual "off-treatment" values will be used in the analysis
- Not study drug-related reasons (e.g., lost to follow-up), then "imputed hypothetical" values, as if subjects had continued receiving study drug, will be used in the analysis

The primary statistical analysis will be performed according to a combination of "treatment-policy strategy" and "hypothetical strategy" in order to account for the different types of intercurrent events.

The Sponsor will put mechanisms in place to ensure that, as much as possible, all subjects are followed and their data are collected, up to and including the Week 24 visit, regardless of their adherence to treatment ("retrieved dropout" strategy). In case missing data are still present, imputation techniques may be considered separately for each treatment arm by using values while the subject was "on-treatment." The primary estimator will be derived by the statistical model described in Section [6.5.5](#) on the dataset completed after multiple imputation. Details of each imputation statistical approach (e.g., the number of imputed datasets created, imputation methodology) will be described in the Statistical Analysis Plan.

6.5.5 Primary Efficacy Analysis

The primary efficacy analysis for this trial will compare balovaptan with placebo at Week 24. The following null (H_0) and alternative (H_a) hypotheses will be tested at a two-sided $\alpha=0.05$ level:

- H_0 : $MEAN_{balovaptan} = MEAN_{placebo}$ versus
- H_a : $MEAN_{balovaptan} \neq MEAN_{placebo}$

for which the $MEAN_{RO}$ and $MEAN_{placebo}$ refer to the mean change from baseline for balovaptan and placebo, respectively.

The analysis of the primary endpoint, the change from baseline at Week 24 on the Vineland-II 2DC score, will be performed by means of analysis of covariance. The model will include the corresponding endpoint baseline score as covariate and treatment, age group, sex, and geographical region as fixed effects. Based on this analysis, least square means, standard errors, treatment difference, and corresponding 95% confidence intervals will be reported.

The effects on continuous secondary endpoints, as well as the short-term effect at 12 weeks will be similarly analyzed.

As a supplementary analysis, a mixed-model repeated measurement (MMRM) analysis, will be performed. The MMRM model will include the corresponding endpoint baseline score as a covariate, with visit, treatment, age group, sex, and geographical region as fixed effects, and treatment by visit interaction; visit will be fitted as a repeated effect with unstructured correlation across visits within each subject.

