6.2 DETERMINATION OF SAMPLE SIZE

The sample size of 350 randomized subjects (175 subjects per arm) provides 85% power to detect a difference in means between treatments in the change from baseline at Week 24 on the Vineland-II 2DC score of at least 4.0 points, assuming a two-sided 5% significance level and a standard deviation of about 12.5 points. A blinded interim analysis of the change in Vineland-II 2DC score from baseline may be performed by the Sponsor to allow an increase in the sample size if necessary to achieve appropriate study power.

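### The supplementary MMRM fits one baseline slope for Weeks 12 and 24; adding a baseline-by-visit term would be a small improvement at almost no cost

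*Combined protocol and SAP*

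**What the plan says.** Section 6.5.5 introduces the model as secondary to the primary ANCOVA: "As a supplementary analysis, a mixed-model repeated measurement (MMRM) analysis, will be performed". It then lists the terms. For baseline: "The MMRM model will include the corresponding endpoint baseline score as a covariate". For the rest: "with visit, treatment, age group, sex, and geographical region as fixed effects, and treatment by visit interaction". For the covariance: "visit will be fitted as a repeated effect with unstructured correlation across visits within each subject". The synopsis (Statistical Methods, Primary Analysis) gives the same list. No baseline-by-visit term appears in either place.

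The primary model is an ANCOVA of the Week 24 change: "The model will include the corresponding endpoint baseline score as covariate and treatment, age group, sex, and geographical region as fixed effects". Because it is fitted at one time point, its baseline slope belongs to Week 24 alone. The Week 12 effect is to be analysed in the same way.

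Three other places matter:
- Appendix 1 schedules the Vineland-II at baseline, Week 12 and Week 24 in the double-blind period, so the mixed model has two post-baseline visits.
- Section 4.2 stratifies randomization on baseline 2DC (below 60 against 60 or above).
- The opening of Section 6 leaves full model detail to a SAP to be finalized before database lock and unblinding. The text available for this review contains no separate SAP.

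**The concern.** With unstructured covariance and a treatment-by-visit term, the model lets nearly everything about the treatment comparison vary by visit except the adjustment for baseline. If change depends on baseline more steeply at Week 24 than at Week 12, the common slope is a compromise. It adjusts too little at Week 24 and too much at Week 12. The unexplained part of the baseline relation enters the Week 24 residual, and a corresponding part of any chance baseline difference between arms enters the Week 24 estimate.

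What is at stake is how cleanly the mixed model can be read beside the primary ANCOVA. With complete data and a baseline-by-visit term, the two would nearly coincide at Week 24. With a common slope they can differ by the slope gap times the baseline imbalance, for a reason unrelated to missing data.

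**Working it through.** **1. The plan's own figure.** Section 6.2 uses a target difference of 4.0, a two-sided 5% level, 175 per arm and "a standard deviation of about 12.5 points". The standard error is 12.5 × √(2/175) = 1.336, and 4.0/1.336 = 2.993. Power is Φ(2.993 − 1.960) = 84.9%, so the stated 85% reproduces.

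**2. Baseline spread.** Section 3.3.3 gives distribution-based estimates, including 0.2 SD and 0.5 SD at baseline, that run from 3.16 to 7.90. Both ends imply the same value: 3.16/0.2 = 7.90/0.5 = 15.8 (Phase II data). The variance is 15.8² = 249.64. One standard error of the between-arm baseline difference is 15.8 × √(2/175) = 1.69 points, before stratification.

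**3. A plausible Week 24 slope.** If the baseline and Week 24 SDs are equal, the correlation is 1 − 12.5²/(2 × 249.64) = 0.69. The slope of change on baseline is then about 0.69 − 1 = −0.31. The documents give nothing comparable for Week 12.

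**4. Assumed inputs (not in the documents).** Slopes at Weeks 12/24 of −0.20/−0.30 and −0.15/−0.35; residual SDs 11 and 11.5; residual correlation 0.6; 15% missing at Week 24, completely at random. The residual variances are 121 and 132.25, the covariance is 0.6 × 11 × 11.5 = 75.9, and the determinant is 121 × 132.25 − 75.9² = 10,241.4.

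**5. Where the common slope lands.** Generalized least squares weights the visits as follows:
- Week 12: 0.85 × (132.25 − 75.9)/10,241.4 + 0.15/121 = 0.005917
- Week 24: 0.85 × (121 − 75.9)/10,241.4 = 0.003743

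The Week 12 share is 0.005917/0.009660 = 0.6125. The gap between the Week 24 slope and the common slope is therefore 0.6125 × 0.10 = 0.061, or 0.6125 × 0.20 = 0.1225.

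**6. Loss of precision at Week 24.** With visit-specific slopes, the per-subject variance is 132.25 × [1 + (0.15/0.85)(1 − 0.6²)] = 147.19. The penalty is gap² × 249.64/147.19:
- Gap 0.06125: 0.94/147.19 = 0.6%
- Gap 0.1225: 3.75/147.19 = 2.5%. This becomes 2.6% when the estimated covariance absorbs the misfit and the gap settles at 0.1233 (3.80/147.19).

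This counts only the baseline imbalance among all randomized subjects. Subjects observed at Week 24 can differ by chance from all those randomized, which adds a little. The regression of Week 24 on Week 12 residuals is 75.9/121 = 0.627, and 0.15 × 0.627 × 0.3875 = 0.0365. The multiplier 0.6125² = 0.375 then becomes (0.6125 + 0.0365)²/0.85 + 0.0365²/0.15 = 0.504. The penalties become 0.504 × 0.10² × 249.64/147.19 = 0.9% and 0.504 × 0.20² × 249.64/147.19 = 3.4%. Even the larger one adds only √1.034 − 1 = 1.7% to the standard error.

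**7. Imbalance passed through.** Per standard error of imbalance: 0.061 × 1.69 = 0.10 points and 0.1225 × 1.69 = 0.21 points, against a 4.0-point target. Stratifying at 60 cuts the standard error of imbalance to about 1.0 to 1.25, if baseline is normal with a mean between 55 and 75. The shift is then about 0.06 to 0.15 points.

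**8. Wider range and simulation.** Complete data were assumed here, with Week 24 slopes of −0.2 to −0.4, Week 12 slopes flatter by 0.05 to 0.20, Week 12 SD 10 to 12.5 and correlation 0.5 to 0.7. The variance penalty runs from 0.1% to 4.4%, the power cost from 0.02 to 1.4 percentage points, and the shift from 0.04 to 0.27 points per unstratified standard error. Selected cases from 4,000 simulated trials each:

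| Slopes, Weeks 12/24 | SE, common slope | SE, slope by visit | Power, common slope | Power, slope by visit |
|---|---|---|---|---|
| −0.3/−0.3 | 1.237 | 1.237 | 0.891 | 0.891 |
| −0.2/−0.3 | 1.244 | 1.236 | 0.886 | 0.891 |
| −0.1/−0.3 | 1.264 | 1.238 | 0.887 | 0.902 |

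(Week 12 SD 12.5 and correlation 0.6 in the first row; 10 and 0.7 in the others.) Across all cases the common-slope means were 3.96 to 4.02 for a true 4.0. Rejection under the null was 4.6% to 5.7%, against 4.9% to 5.9% with slopes by visit.

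**The case against.** The strongest reply is that this is a modelling preference for a supplementary analysis, with no documented harm. The documents give no visit-specific slope, no Week 12 SD and no correlation, so nothing shows that the slopes differ. Baseline is still adjusted for, and randomization is stratified on it. Section 6 also defers detail to the SAP, which may add the term. The first three of these stand and fix the size of the point. The last is weaker: Section 6.5.5 already names every term and the covariance structure, so a SAP that follows it inherits the common slope.

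A reader might infer that the Week 24 contrast is left exposed to baseline imbalance. The documents do not support that. Only the slope gap times the imbalance passes through, and there is no unconditional bias.

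A reader might also infer that, with the term added, any disagreement between the mixed model and the ANCOVA would diagnose missing data. That is not supported either. Section 6.5.4 makes the primary estimator an ANCOVA after multiple imputation, under a mixture of treatment-policy and hypothetical strategies. The two analyses can disagree for those reasons whatever the slope. The term removes one source of disagreement, not all of them.

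In favour of the change, the exploratory models in Section 6.5.7 already carry a subgroup-by-time term, and baseline 2DC category is one of the subgroups. The plan thus lets the role of baseline vary over time there, but not in the model on which those analyses build.

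**Conclusion.** The point holds as a conditional refinement of a supplementary analysis. As listed, the mixed model has one baseline slope. If the true slopes differ by 0.10 to 0.20, the cost at Week 24 is a few percent of variance at most and a shift of a tenth or two of a point for a typical chance imbalance. If they are equal, the cost is zero.

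The slopes, residual SDs, correlation and missingness are all assumed. The baseline SD is inferred from Phase II figures. The primary ANCOVA and the separate Week 12 analysis do not depend on this term, and the trial's conclusion would not turn on it. Severity is the lowest.

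**What to change.** Add a baseline-by-visit interaction to the mixed model in Section 6.5.5, in the matching synopsis text and in the SAP. Carry it into any exploratory mixed model under Section 6.5.7 that is built on the same terms. Changing Section 6.5.5 alone would leave the synopsis inconsistent.

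With two post-baseline visits the cost is one degree of freedom among about 350 subjects. When the slopes are equal, the simulated standard error is unchanged. Sample size, data collection and the primary analysis stay as they are. The term should be written in before unblinding, since adding it later would look driven by the data.

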6.5.6 Secondary Efficacy Analyses

Similar hypotheses will also be tested for the secondary continuous efficacy parameters. Methods for controlling the type I error in the testing of secondary endpoints as well as their hierarchical order will be described in the Statistical Analysis Plan.

Categorical endpoints, such as the CGI-I and change from baseline of CGI-S, will be analyzed by means of logistic regression after dichotomizing the results into two categories (improved and not improved), considering the CGI-S baseline value as a covariate, and treatment, age group, sex and geographical region as factors. Logistic regression will be performed also for the responder endpoint, considering the Vineland-II 2DC score at baseline as a covariate, and treatment, age group, sex, and geographical region as factors.

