3. STUDY DESIGN

3.1 DESCRIPTION OF THE STUDY

Study WN39434 is a Phase III, randomized, double-blind, placebo-controlled, parallel-group, multicenter, 24-week, efficacy, and safety study of 10 mg of oral balovaptan QD in adults (18 years old or older) with ASD, followed by a 2-year open-label extension period for subjects completing the double-blind treatment period.

Subjects providing informed consent will undergo screening within 4 weeks prior to the first double-blind study drug (balovaptan or placebo) administration. Eligible subjects will be randomized in a 1:1 ratio in a blinded fashion to either 10 mg of balovaptan or matching oral placebo QD for 24 weeks. The primary efficacy endpoint is the change from baseline at Week 24 on the Vineland-II two-domain composite (2DC) score.

Thus, for subjects remaining in the full study, the approximate length of the study will be 144 weeks or 34 months (screening [approximately 4 weeks], double-blind treatment [24 weeks], and open-label extension period [104 weeks] with a safety follow-up period of 12 weeks after completion of double-blind treatment period or open-label extension period).

Subjects will be recruited from international sites, including sites in North America and limited rest of the world (ROW) countries. Subjects who prematurely discontinue from study treatment or from the study will not be replaced. However, all subjects should be followed and their data (specifically, vital sign measurements, adverse events, concomitant treatment, Vineland-II, CGI-S, CGI-I, PedsQL 4.0 Core) collected up to and including the Week 24 visit, regardless of their adherence to treatment.

Randomization will be stratified by baseline 2DC score of the Vineland-II score (<60 vs. ≥60), sex (male vs. female), geographical region (North America vs. ROW), and age (<25 years vs. ≥25 years). The main analysis of the primary and secondary efficacy endpoints will occur once the final data from all visits, up to and including Week 24, have been collected and cleaned, and the database has been locked. An interim futility analysis *will* be performed by an independent Data Monitoring Committee (iDMC) when approximately 50% of subjects complete the Week 24 visit.

The iDMC will meet regularly to oversee safety throughout the trial and its activities will be described in a separate iDMC charter (see Section 3.1.1.5 for further details).

[figure not shown]

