3.3.4 Rationale for Subject Population

Study WN39434 will include both males and females. The prevalence of ASD has been reported to be approximately 1 in 42 boys and 1 in 189 girls (CDC 2016). Furthermore, females with impairments in social and communication function are typically more intellectually impaired and are less likely to meet the eligibility criteria stipulating an IQ score ≥ 70 ; only 1 in 8 to 9 ASD subjects with IQ score ≥ 70 is reported to be female (Fombonne et al. 2011; Stacy et al. 2014). Therefore, the proportion of females who would be recruited is expected to be approximately 12% of the total study population. To ensure that the subject population is representative of ASD epidemiology the proportion of female subjects will be limited to a maximum of 20% of the entire study population. Randomization of subjects will be stratified by sex.

Study WN39434 is designed as an international study that will recruit subjects from regions, including North America and the ROW. The proportion of subjects from the ROW is expected to be approximately 20% of the total study population. Randomization of subjects will be stratified by region (North America vs. ROW) to increase the reliability of subgroup analyses within each region.

To limit the impact of diagnostic heterogeneity, eligible male and female subjects ages ≥ 18 must meet Diagnostic and Statistical Manual of Mental Disorders, Version 5 (DSM-5) criteria for ASD, which will be confirmed using the ADOS-2. The ADOS-2 is a semi-structured, standardized assessment of communication, social interaction, play/imaginative use of materials, and restricted and repetitive behaviors in ASD and is referred to as the "gold standard" observational assessment for diagnosing ASD (Ozonoff et al. 2005; Kanne et al. 2008).

Subjects with confirmed ASD who are exhibiting impairments in social communication will be studied. For this study, the SRS-2 will be performed during screening; only subjects with a study partner-completed (proxy) SRS-2 total *t*-score ≥ 66 , consistent with moderate or severe symptoms, will be randomized. These assessments ensure that subjects demonstrate relevant deficits in social communication and social interactions and that, collectively, these symptoms result in a moderate-to-severe phenotype.

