4.2 METHOD OF TREATMENT ASSIGNMENT AND BLINDING

Approximately 350 subjects will be randomized to receive either placebo or 10 mg of oral balovaptan QD in a 1:1 ratio. An independent interactive voice or web-based response system (IxRS) provider will conduct randomization and hold the treatment assignment code. Randomization will be stratified by a subject's baseline Vineland-II 2DC score (<60 vs. ≥60), sex (male vs. female), region (North America vs. ROW), and age (<25 years vs. ≥25 years).

There will be no replacement of subjects should a subject's treatment be discontinued for any reason.

Study site personnel and subjects will be blinded to treatment assignment during the study. The Sponsor and its agents will also be blinded to treatment assignment, with the exception of individuals who require access to subject treatment assignments to fulfill their job roles during a clinical trial.

If unblinding is necessary for a medical emergency (e.g., in the case of a serious adverse event for which subject management might be affected by knowledge of treatment assignment), the investigator will be able to break the treatment code by contacting the IxRS. The investigator is not required to contact the Medical Monitor prior to breaking the treatment code; however, the treatment code should not be broken except in emergency situations. If unblinding occurs, subjects should not continue receiving study drug and should proceed to the end-of-treatment visit and subsequently safety follow-up.

If the investigator wants to know the identity of the study drug for any reason other than a medical emergency, he or she should contact the Medical Monitor directly. The investigator should document and provide an explanation for any non-emergency unblinding. The investigator will be able to break the treatment code by contacting the IxRS.

Whenever disclosure of the identity of the study drug is necessary, adequate procedures will be put in place to ensure integrity of the data. Any unblinding at the investigational site will be documented in the study report with the date, the reason for identifying the drug, and the name of all person(s) who were unblinded.

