6. STATISTICAL CONSIDERATIONS AND ANALYSIS PLAN

Database lock to enable the analysis of the 24-week, placebo-controlled phase of the study will occur once all subjects have either completed the 24-week assessment or withdrawn from the study early, and all data required for analysis have been cleaned and verified. After database lock, treatment assignments will be unblinded to the Sponsor.

The final analysis of the 24-week placebo-controlled period will be performed after database lock. The final analysis of all data collected in the study, including the open-label extension, will occur after all subjects have completed the study.

Details of the planned statistical analyses mentioned below in this section will be fully specified in the Statistical Analysis Plan, which will be finalized prior to the locking the study database and unblinding the study.

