6.5.7 Subgroup Analyses

The results of selected efficacy variables will be summarized within subgroups using descriptive statistics. The following variables will be used to define the subgroups:

- Baseline 2DC score of the Vineland-II (<60 vs. ≥ 60)

- Sex (male vs. female)
- Geographical region (North America vs. ROW)
- Age (<25 years vs. ≥25 years)

Additional exploratory analyses of efficacy results may be performed using an MMRM model, with subgroup, treatment-by-subgroup interaction, and subgroup-by-time interaction terms included along the independent effects described above. Such exploratory analyses will be performed if the descriptive statistics results indicate substantial differences between the subgroups.

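### Baseline Vineland-II 2DC is a randomization factor but is not listed in the secondary models whose endpoint is not 2DC; adding it would give a small gain at almost no cost

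*Combined protocol and SAP*

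**What the plan says.** Section 3.1 states: "Randomization will be stratified by baseline 2DC score of the Vineland-II score (<60 vs. ≥60), sex (male vs. female), geographical region", and adds age (<25 vs. ≥25 years) as the fourth factor. Section 4.2 repeats this: "Randomization will be stratified by a subject's baseline Vineland-II 2DC score".

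For the primary ANCOVA, Section 6.5.5 says: "The model will include the corresponding endpoint baseline score as covariate and treatment, age group, sex, and geographical region as fixed effects". There the endpoint's own baseline is the 2DC, so all four randomization factors are represented. The same section then says: "The effects on continuous secondary endpoints, as well as the short-term effect at 12 weeks will be similarly analyzed". Read with the preceding sentence, each continuous secondary endpoint gets its own baseline in place of the 2DC.

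For the dichotomized CGI-I and CGI-S change, Section 6.5.6 specifies logistic regression "considering the CGI-S baseline value as a covariate, and treatment, age group, sex and geographical region as factors". The logistic model for the ≥6-point responder endpoint does include baseline 2DC.

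Section 6.5.7 lists "Baseline 2DC score of the Vineland-II" among the subgroup variables, but for descriptive summaries. Section 6 defers the rest: "Details of the planned statistical analyses mentioned below in this section will be fully specified in the Statistical Analysis Plan". The text of that separate SAP is not part of the document reviewed.

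**The concern.** The plan adjusts for three of its four randomization factors in every model and for the fourth only where 2DC is the endpoint's own baseline. It gives no reason for the difference. The secondary endpoints mainly affected are PedsQL Core, HAM-A, Daily Living Skills, CGI-I and CGI-S change.

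Stratifying balances the arms on 2DC and so removes the between-stratum component from the sampling variance of the treatment difference. A linear model without 2DC still counts that component in its residual variance. If 2DC predicts the outcome beyond the listed covariates, the standard error is therefore too large, the test is conservative and some power is lost. If 2DC is not prognostic, nothing is lost. What is at stake is efficiency and consistency in the secondary endpoints. The validity of the trial and the primary result are not in question.

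**Working it through.** **The plan's own figure.** Section 6.2 gives 175 per arm, a 4.0-point difference, SD 12.5 and two-sided 5%. The standardized effect is 4.0/12.5 = 0.32. The noncentrality is 0.32/√(2/175) = 2.993, and power is Φ(2.993 − 1.96) = 84.9%. The stated 85% is reproduced.

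**Inputs for the check.** From the documents: N = 350, 1:1 allocation, the four factors, 20% of subjects from the rest of the world, and in Section 3.3.4 "the proportion of females who would be recruited is expected to be approximately 12% of the total study population". Assumed, because the documents give no figure: blocks of 4 within the 16 strata, 30% of subjects with 2DC <60, 50% aged <25, and the prognostic strength of 2DC. That strength is expressed as a partial R² of 0, 2, 5 or 10% of the residual variance of the planned model. No secondary endpoint has a stated effect or power, so 0.32 SD is borrowed from the primary and 0.20 SD is added as a smaller case.

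**Closed form for the linear models.** Let k be the share of the 2DC effect that stratification balances.

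- k = 1 if the <60/≥60 stratum itself is what predicts outcome.
- If a normally distributed continuous 2DC predicts outcome, a 30/70 split captures k = φ(z₀.₃)²/(0.3 × 0.7) = 0.348²/0.21 = 0.576.
- Actual type I error of the planned test: 2Φ(−1.96/√(1 − kR²)).
- Power of the planned test: Φ((2.993 − 1.96)/√(1 − kR²)).
- Power with 2DC added: Φ(2.993/√(1 − R²) − 1.96).

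At R² = 10%, adding 2DC gives Φ(3.155 − 1.96) = 88.4%.

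- k = 1: type I error is 2Φ(−1.96/√0.9) = 3.9%. Planned power is Φ(1.033/0.949) = 86.2%, so the gain is 2.2 points.
- k = 0.576: type I error is 2Φ(−1.96/√0.9424) = 4.35%. Planned power is Φ(1.033/0.971) = 85.6%, so the gain is 2.8 points.

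**Simulation of the linear models** (10,000 trials per setting; gains taken before rounding, so they can differ by 0.1 from the rounded powers):

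| Partial R² | 0% | 2% | 5% | 10% |
|---|---|---|---|---|
| Stratum prognostic, stratum added: gain at 0.32 SD | 0 | 0.5 | 1.3 | 2.3 |
| Same, gain at 0.20 SD | 0.1 | 0.9 | 1.8 | 4.1 |
| Type I error, planned test | 5.0% | 4.8% | 4.7% | 3.7% |
| Continuous 2DC prognostic, continuous added: gain at 0.32 SD | 0.1 | 0.7 | 1.4 | 2.9 |
| Same, gain at 0.20 SD | 0 | 1.0 | 1.8 | 4.3 |
| Type I error, planned test | 4.7% | 5.0% | 4.7% | 4.3% |

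With a non-prognostic 2DC, power at 0.32 SD is 0.845 either way with the stratum added, and 0.843 against 0.844 with continuous 2DC.

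A separate simulation (3,000 trials) at partial correlation 0.3, that is R² 9%, gave 83.8% without and 86.7% with 2DC. At a partial correlation of 0.5 the figures were 85.9% and 93.5%. Such a value seems unlikely once the endpoint's own baseline is in the model.

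**Overlap for the Vineland endpoints.** 2DC is the mean of Communication and Socialization, so those baselines already carry much of it. With equal weights and an assumed inter-domain correlation r of 0.5 to 0.8, the share of 2DC variance not in the endpoint's own baseline is:

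- Communication or Socialization: 1 − (1 + r)/2 = 25% to 10%.
- Composite: 1 − 2(1 + 2r)/(3(1 + r)) = 11% to 4%.
- Daily Living Skills: 1 − 2r²/(1 + r) = 67% to 29%.

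For a 2DC effect worth R² 10% without overlap, simulated gains at 0.32 SD (8,000 trials) are about 0.8 to 0.3, 0.4 to 0.1 and 1.8 to 1.0 points respectively.

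**Logistic models** (6,000 trials, assumed treatment log odds ratio 0.58 conditional on the stratum):

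| Stratum log odds ratio | 0 | 0.5 | 0.8 | 1.2 |
|---|---|---|---|---|
| Power, planned | 0.755 | 0.747 | 0.733 | 0.692 |
| Power, stratum added | 0.756 | 0.753 | 0.747 | 0.718 |
| Gain, points | 0.1 | 0.5 | 1.4 | 2.7 |
| Type I error, planned | 4.9% | 4.8% | 4.8% | 3.8% |

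A second set (1,500 trials, treatment log odds ratio 0.65, continuous 2DC with log odds ratio 0, 0.3 or 0.6 per SD) gave 83.5% against 83.1%, 81.2% against 81.7%, and 77.0% against 80.9%. Monte Carlo error there is about 1 point.

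**The case against.** The strongest reply is that nothing here is an error. The planned tests are valid, no secondary endpoint has a power target, and the separate SAP may already add the term. That is correct. The point concerns only the covariates the protocol lists, and it ranks as an optional improvement.

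The benefit also rests wholly on assumed prognostic strength. At R² of 2% the linear gain is 1 point or less, and the 2-to-4-point gains need R² of 10%, a partial correlation of about 0.32. The CGI models already adjust for baseline CGI-S, a clinician's global severity rating. A stratum log odds ratio of 1.2 on top of that (odds ratio about 3.3) is an upper scenario. Overlap between CGI-S and 2DC was not worked out, and the main simulations assume 350 complete subjects. All of this stands, and it limits the size of the gain.

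Third, the change is not entirely neutral for the logistic endpoints. The odds ratio becomes conditional on one more covariate. In the strongest case of the first set, the mean fitted log odds ratio was 0.548 without and 0.592 with the stratum. These are two different targets (non-collapsibility), and the difference does not show that the planned estimate is biased. It does mean the choice must be fixed before unblinding.

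Finally, for Communication, Socialization and the composite the gain is negligible. Including them is justified only by having one rule for all endpoints.

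**Conclusion.** The concern holds as a minor point. On the protocol's wording, one of the four randomization factors is absent from the models for PedsQL Core, HAM-A, Daily Living Skills, CGI-I and CGI-S change, and nominally also from those for Communication, Socialization and the composite. Omission does not inflate type I error; at R² 10% the planned linear test runs at roughly 3.7 to 4.4% instead of 5%. The power given up is 0 to about 4 points in the linear models for partial R² of 0 to 10%, and 0.1 to 2.7 points in the main logistic scenarios (3.9 in the strongest case of the second set). The primary analysis, the Week 12 2DC analysis and the responder model are unaffected. These sizes depend on the assumed prognostic strength, the assumed 30% of subjects below 60 and, for the linear models, the effect sizes used. Confidence is medium because the documents give no prognostic figure and the separate SAP could not be read.

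**What to change.** State in Sections 6.5.5 and 6.5.6, and in the SAP, that every secondary efficacy model not already adjusting for baseline Vineland-II 2DC also includes it because it is a randomization factor. Apply this uniformly at Weeks 12 and 24.

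Name one form in advance. Either works, but the continuous score is preferable: with a prognostic continuous 2DC at R² 10% and 0.32 SD, power was 0.857 as planned, 0.872 with the stratum and 0.886 with the continuous score. Keep all other terms, and the logistic regression on improved versus not improved, as they are.

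The cost is one sentence per section and one residual degree of freedom, with no new data, since 2DC must be known to randomize each subject. The text should say that the logistic odds ratio is then conditional on 2DC as well, and the change should be fixed before unblinding. If the SAP already contains the term, only the protocol wording needs aligning.
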